**18/01/2018**

# Introduction

Caesarian section delivery has become more prevalent than the vaginal delivery in Egypt. According to the Demographic and Health Survey (DHS) in 2014, 52 % of women in Egypt give birth by caesarian section. This makes the caesarian section one of the commonest abdominal surgeries in Egypt.

Many complications could occur after an abdominal surgery. So after a caesarian section, complications that are variable in its intensity could occur. One of the commonest but yet serious is the postoperative ileus. (**Sunil et al, 2001**). Postoperative ileus complicates 26-31% of caesarian section deliveries. (**Teoh et al, 2007**)

Postoperative ileus is a predictable delay in gastrointestinal motility that occurs after abdominal surgery. Probable causes include disruption of the sympathetic/parasympathetic pathways to the gastrointestinal tract, inflammatory changes through multiple pathways, and the use of opioids for the management of postoperative pain. (**Artinyan et al, 2011**)

Postoperative ileus is presented with nausea, vomiting, abdominal distention, abdominal tenderness, and delayed passage of flatus and stool. These symptoms would remarkably worsen the patients' quality of life, increase length of hospital stay, and increase costs associated with postoperative recovery. (**Holte et al, 2002**)

Although ileus is so prevalent, preventative therapeutic options are still limited. Many trials have been made to prevent ileus, including administration of prokinetic drugs such as serotonin receptor antagonists (**Toyomasu et al, 2011**), neostigmine (**Drake et al, 2016**), alvimopan (**Tan et al, 2007**), and ghrelin agonists (**Beck et al, 2014**), early resumption of feeding (**Zhuang et al, 2013**), gum chewing (**Ertas et al, 2013**) and adequate pain control (**Bragg et al, 2015**) ,Unfortunately, none of these strategies has been completely successful.

Coffee is one the most popular drinks in Egypt and the whole world. Several researches were done worldwide to study the effect of the caffeine present in coffee and resumption of intestinal motility after various abdominal surgeries. (**Brown et al, 1990**) (**Müller et al, 2012**). Recently the effect of coffee on prevention of postoperative ileus after caesarian section was researched (**Rabiepoor et al, 2017**).

That's why we are concerned in our study to determine the efficacy of coffee in prevention of postoperative ileus.

## **Aim of the Work**

This study aims to assess the value of drinking coffee in promoting intestinal motility and prevention of postoperative ileus after elective caesarean section.

### **Research question:**

After elective caesarean section, can drinking coffee lead to early intestinal motility and prevent postoperative ileus?

### **Research hypothesis:**

Drinking coffee promotes intestinal motility thus prevent postoperative ileus and improve the postoperative intestinal symptoms after elective caesarean section.

### **Primary outcome:**

- A change in the number of hours for the patients to pass flatus for the first time after an elective caesarean.

### **Secondary outcomes:**

- A change in the number of hours for the patients to have their first intestinal sound to be heard by a stethoscope.
- A difference in the number of hours for the patients to pass stool.
- A difference in the number of the patients' hospital stay hours.

# **Patients and Methods**

This study will be conducted in the 1 year period starting from October 2017, at Ain Shams Maternity Hospital.

## **Patients:**

Patients will be recruited from emergency unit and inpatient wards in Ain Shams University maternity hospital.

### **Inclusion criteria:**

- 1- Caesarean section.
- 2- Spinal anesthesia.
- 3- Total surgery time less than 90 minutes.

### **Exclusion criteria:**

- 1- Previous complicated abdominal surgery or caesarean section with extensive adhesions requiring extensive dissection or intestinal manipulation.
- 2- Intraoperative intestinal complications.
- 3- Intraoperative respiratory complication.
- 4- Chronic intestinal diseases: irritable or inflammatory bowel diseases.
- 5- Chronic diarrhea or constipation.
- 6- Using laxatives pre-operatively.

7- Known hypersensitivity to caffeine.

8- Thyroid or hepatic disease.

9- Cardiac arrhythmias.

## **Methods:**

### **Study type:**

A single blinded, randomized, placebo-controlled trial.

### **Sample Size Justification:**

According to The number of samples was calculated according to a study by Müller et al, (2010) considering the power of 90%, confidence 95% and significant level of 0.05, the sample size needed is 544 cases, and with adding 10% for occasional cases' drop out so the total sample size would be 600 cases, divided into two groups, 300 patients each, one in the intervention group and the other is the placebo.

### **Study design:**

This study will include 600 patients undergoing their caesarean section.

The study aims will be explained to all patients and an informed written consent will be taken.

All recruited patients will be divided into two groups according to a random selection by the primary researcher who consecutively will open sequentially numbered, opaque, sealed envelopes containing colored

cards, blue card group will represent the intervention group and the red card group will represent the placebo group.

### **Procedure:**

- For all patients, the anesthetic used will be Marcaine® Spinal heavy 0.5% and fentanyl and for post-operative pain, ketorolac will be used.
- Through Pfannenstiel incision, transverse lower segment uterine incision is done, with the duration of the surgery not exceeding 90 minutes.
- Patients will not be permitted to drink or eat, except for the drink offered by the researcher, till passing flatus.
- Early ambulation was encouraged.
- A stethoscope will be used to detect the first intestinal movement each 15 mins after the surgery.
- The patients will be advised to notify the researcher when they pass both flatus and feces.

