### **Intervention:**

[figure not shown]
- The intervention plan will be performed within the first 24 hours after the surgery.
- Provided by the researcher within 10 minutes, patients will drink 100cc sugar-free coffee at 3, 6 and 9 hours after the surgery, and the control group will drink 100cc sugar-free decaffeinated coffee at the same intervals.
- No other liquid will be allowed till passage of flatus and feces in the first day of surgery.
- We will use Nescafe Gold ® coffee (10g per 100cc water) for all the patients in the intervention group.

- We will use Nescafe Gold DECAF coffee (10g per 100cc water) for all the patients in the control group.

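### First flatus, the primary outcome, is captured only by an unprompted notice whose wording ties it to stool, so it can be timed late

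*Combined protocol and SAP*

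**What the plan says.** The Primary outcome section defines the endpoint as "A change in the number of hours for the patients to pass flatus for the first time after an elective caesarean". Secondary outcomes lists stool separately: "A difference in the number of hours for the patients to pass stool".

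The only statement of how either time is obtained is in Procedure: "The patients will be advised to notify the researcher when they pass both flatus and feces". The protocol describes no scheduled question about flatus, no diary, no instruction to note the clock time and no rule for delayed or overnight reports.

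Bowel sounds, also a secondary outcome, do have an active check: "A stethoscope will be used to detect the first intestinal movement each 15 mins after the surgery".

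Two passages on food and drink bear on how the notice should be read. Procedure says "Patients will not be permitted to drink or eat, except for the drink offered by the researcher, till passing flatus". Intervention says "No other liquid will be allowed till passage of flatus and feces in the first day of surgery".

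**The concern.** The primary outcome is an event time, so it is only as good as the moment at which the event is recorded. Here that moment is left to the woman. She must notice the event, be awake and call the researcher, and the sentence that instructs her can be understood as asking for one call after both events.

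The secondary outcome that a stethoscope can detect is therefore measured more closely than the outcome on which the trial will be judged. If flatus times are late or recalled, the t-test in Data Analysis compares the true times plus a reporting delay, and nothing in the plan detects or handles that delay. An event time not captured at the bedside cannot be recovered later.

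**Working it through.** **Step 1: the two readings of the notice.**

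| Reading | What is recorded as flatus time | Consequence |
|---|---|---|
| One notice, once both events have occurred | Time of stool, or a recalled time | The primary outcome merges with the secondary outcome of time to stool |
| A notice at each event | Time of the woman's call | Outcomes stay distinct, but timing depends on an unprompted report |

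Flatus can be timed late under either reading. The first is worse.

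**Step 2: does the rest of the protocol settle the reading?** The restriction in Procedure ends at flatus. It can be applied only if flatus is known when it happens, which favours a notice at each event. The restriction in Intervention is tied to flatus and feces together, which fits a joint notice. The two passages differ and must be reconciled; as they stand they do not decide the matter.

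**Step 3: what the plan's own figures allow.** Sample Size Justification gives 544 evaluable women, 90% power and a significance level of 0.05, then 600 after a 10% allowance. The allowance reproduces approximately: 544 × 1.10 = 598.4 and 544 / 0.90 = 604.4. The 544 itself cannot be reproduced, because no effect size or SD is stated. Working backwards with 544 / 2 = 272 per arm and a two-sided test (sidedness is not stated, so this is assumed):

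implied standardised difference = (1.960 + 1.282) × √(2/272) = 0.278.

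That is 1.1 h, 2.2 h or 3.3 h if the outcome SD is 4, 8 or 12 h.

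**Step 4: power lost to delay that is equal on average in both arms.** Assumptions: outcome SD s of 4 to 12 h, and an additive delay, independent of the true time, with SD e of 2 to 6 h. None of these values is in the documents. With true difference 0.278 × s,

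power = Φ( 0.278 s / [√(s² + e²) × √(2/272)] − 1.960 ).

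For example, with s = 4 and e = 4, the first term is 3.242 / √2 = 2.292, and Φ(2.292 − 1.960) = Φ(0.332) = 63%.

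| Outcome SD (h) | Delay SD 2 h | Delay SD 4 h | Delay SD 6 h |
|---|---|---|---|
| 4 | 83% | 63% | 44% |
| 8 | 88% | 83% | 74% |
| 12 | 89% | 87% | 83% |

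The loss is small when the delay varies little relative to the outcome, and serious when the two are similar.

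**The case against.** The strongest reply is that the joint reading is strained. Flatus and stool are defined as separate timed outcomes, and the restriction in Procedure presupposes that flatus is known when it occurs, so the natural sense is a notice at each of the two events. Women who are fasting until flatus also have a reason to report it promptly, and staff are at the bedside for auscultation and for the drinks.

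Much of this stands. The each-event reading is the more natural one, and the incentive is real, although it does nothing for a sleeping woman and could also prompt early reports. But the wording in Intervention leaves the reading open, and no section says that flatus is asked about at any contact.

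A reader might go further and infer that caffeine keeps women awake, so that controls report later and coffee appears to work when it does not. The arms do differ in caffeine, since "the control group will drink 100cc sugar-free decaffeinated coffee at the same intervals", and blinding the patient would not remove such an effect. But the documents discuss coffee only in relation to the gut. They say nothing of sleep, operating hours or night-time reporting. Nor does "The intervention plan will be performed within the first 24 hours after the surgery" set an observation window; it concerns when the intervention is given. Any false-positive rate built on this chain would combine an assumed share asleep, an assumed delay and an assumed SD, so none should be claimed.

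**Conclusion.** The point holds as a measurement weakness in the primary outcome. One sentence governs capture; one of its readings times flatus at stool, and the other leaves the time to an unprompted report.

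The supported consequence is added error and reduced power. Its size depends on an outcome SD and a delay SD that the documents do not give. Over the assumed ranges, power falls from the planned 90% to between 89% and 44%. These figures also assume a two-sided test, a true difference equal to the one implied by 272 per arm, and a delay that is additive, independent of the true time and equal on average in the two arms.

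A difference in reporting between arms, for example through wakefulness, remains a possibility. It is an inference, and the documents do not support a statement of its size or direction.

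**What to change.** - Reword the sentence in Procedure so that women notify the researcher at once at first flatus, and again, separately, at first stool. Record the clock time of each event and of the end of surgery.
- At contacts that already exist (the auscultation rounds while they last, and the drinks at 3, 6 and 9 h), ask one scripted question on whether flatus has been passed, identical in both arms. Record the time of the last negative and first positive answer.
- Where possible, have the question asked by existing staff who have not seen the allocation card. Study design has the primary researcher open the envelopes, and Study type does not say who is blinded.
- Prespecify a sensitivity analysis of the primary outcome that treats flatus as having occurred between the last negative answer and the report.
- Reconcile the two restriction statements in Procedure and Intervention.

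The cost is a reworded instruction, a few case report form fields, slightly longer contacts and one extra analysis. There is a limit: auscultation looks only for the first bowel movement sound and the last drink is at 9 h, so scheduled contact may end there. Later events would have wide intervals and would still rely on the woman's own prompt notice.

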### **Intervention:**

[figure not shown]
- The intervention plan will be performed within the first 24 hours after the surgery.
- Provided by the researcher within 10 minutes, patients will drink 100cc sugar-free coffee at 3, 6 and 9 hours after the surgery, and the control group will drink 100cc sugar-free decaffeinated coffee at the same intervals.
- No other liquid will be allowed till passage of flatus and feces in the first day of surgery.
- We will use Nescafe Gold ® coffee (10g per 100cc water) for all the patients in the intervention group.

- We will use Nescafe Gold DECAF coffee (10g per 100cc water) for all the patients in the control group.

### History taking:

- Age, parity, gestational age at time of delivery.
- Cause of caesarean section.
- Any past medical history or drug intake.

### THE TRIAL FLOW CHART

## **Data Analysis:**

Data analysis will be performed by SPSS 16.0 using descriptive statistics tools, including mean, standard deviation and figures. A t-test will be used to compare mean values of the two groups. P-values, smaller than 0.05, were considered statistically significant.

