### **Confidentiality:**

Only the patient file numbers and patient initials will be recorded in the case report form.

The researcher will keep a patient identification list (patient number and corresponding names and contacts) to enable records to be identified and enable records to be identified and allow communication with the patients.

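### Time to first stool is compared by a t-test on means, but no readable text says when observation ends or how a woman with no recorded stool is analysed

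*Combined protocol and SAP*

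**What the plan says.** - **Outcome.** The secondary outcomes include "A difference in the number of hours for the patients to pass stool" and, separately, a between-group difference in "hospital stay hours".
- **How stool is recorded.** Under Procedure: "The patients will be advised to notify the researcher when they pass both flatus and feces". No end time is attached to this.
- **Analysis.** Data Analysis names means, standard deviations, figures, a 0.05 threshold and one test: "A t-test will be used to compare mean values of the two groups". It names no time-to-event method, censoring rule or missing-data rule.
- **Nearest time limits.** The Intervention section has a 24-hour window for giving the drinks and a fluid rule: "No other liquid will be allowed till passage of flatus and feces in the first day of surgery". Neither says when stool stops being recorded.
- **Dropout.** Sample Size Justification states that "the sample size needed is 544 cases" and adds 10% for dropout. That enlarges the trial but gives no rule for analysing the women concerned.
- **Contacts.** Confidentiality provides for an identification list to "allow communication with the patients", but no calls are scheduled.

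The trial flow chart, which sits directly above Data Analysis, and a figure under Intervention are not shown in the text available. A follow-up time could stand in either.

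**The concern.** Time to stool is a time to an event that may not have happened, or may not have been reported, when a woman goes home. A t-test on means needs one number per woman. For a woman with no recorded stool the analyst must either leave her out or assign a time, most naturally her discharge time. The plan leaves that choice open until the data are in hand.

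The choice matters because stay may differ by arm; the trial itself looks for such a difference. Suppose observation stops at discharge. If coffee women go home earlier, their late stool times are cut off sooner and coffee looks faster even with no effect on stool. If they stay longer, a real benefit can disappear. If stays are equal, the late times are trimmed more heavily in the slower arm, so a real difference is understated.

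**Working it through.** **The plan's figure.** 544 × 1.10 = 598.4, rounded to 600; 544 / 2 = 272 per arm. The 544 cannot be reproduced, because no effect size or standard deviation is given. It is used below only as the arm size.

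**Assumptions (not in the documents).**
- Stool times are log-normal with SD(log) 0.5.
- Discharge times are normal with SD 6 h, independent of stool time unless stated.
- Stool is recorded only if it comes before discharge.
- Tests are two-sided at 0.05, with 4,000 simulated trials per scenario (Monte Carlo standard error at most 0.8 points).

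**Share unobserved.** Ignoring the spread of discharge times, the share with no stool by mean discharge time L is 1 − Φ(ln(L / median) / 0.5). With a 30 h median:
- L = 36: 1 − Φ(0.365) = 36%
- L = 32: 1 − Φ(0.129) = 45%

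Adding the 6 h spread gives the 37% and 46% in the table.

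**No true effect (medians 30 v 30 h).** False-positive rates, with discharge and unobserved shares given as control v coffee:

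| Mean discharge | Unobserved | t-test, drop | t-test, set to discharge | Log-rank |
|---|---|---|---|---|
| 36 v 36 h | equal | 4.6% | 5.4% | 5.1% |
| 36 v 34 h | – | 14% | 20% | 5% |
| 36 v 32 h | 37% v 46% | 42% | 68% | 4% |
| 48 v 44 h | 18% v 24% | 20% | 13% | 5% |
| 60 v 56 h | 9% v 11% | 10% | 6% | 5% |
| 72 v 68 h | 4% v 5% | 7% | 5% | 5% |

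Reversing the gap (32 v 36 h) gives 42% / 67% / 5%, with every false t-test result against coffee.

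**Real effect (medians 30 v 26 h).** The mean of a log-normal is the median × exp(0.5²/2) = median × 1.133, so the true mean difference is 4 × 1.133 = 4.5 h.

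| Mean discharge | Estimate, drop / set to discharge | Rejection, drop / set / log-rank |
|---|---|---|
| 36 v 36 h | 1.6 / 2.2 h | 49% / 85% / 85% |
| 48 v 48 h | 2.3 / 3.2 h | 69% / 90% / 86% |
| 72 v 72 h | 3.5 / 4.2 h | 83% / 89% / 86% |
| 32 v 36 h (coffee later) | 0.1 / 0.6 h | 5% / 13% / 83% |

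**Sensitivity to the assumptions (no effect; drop / set to discharge).**
- Shorter median, 36 v 32 h: 32% / 31% at 24 h; about 19% / 11% at 18 h.
- 18 h median, 48 v 44 h: 8% / 6%.
- SD(log) 0.3 or 0.7, 30 h median, 36 v 32 h: 49% / 80% and 32% / 58%.
- A different model (gamma times, mean 30 h, SD 10 h, 300 per arm, control stay 36 h): with coffee stay 3 h shorter 32% / 40%, 3 h longer 28% / 24%, and equal about 5%.

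**If discharge depends on bowel recovery.** At 36 v 32 h with no effect, log-rank censored at discharge rejects in 6.7% (correlation 0.3) to 8.5% (correlation 0.5) of trials. So log-rank alone is not a complete repair.

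**If women are called up to 96 h (correlation 0.5; drop / set / log-rank).**
- 90% reached: false positives 4.6% / 5.1% / 4.9% and power 85% / 87% / 86%.
- 70% reached: false positives 4.5% / 6.8% / 4.4% and power 80% / 86% / 85%, with t-test estimates still low at 3.6 and 3.8 h.

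**The case against.** **The t-test is not the root of the problem.** This stands in part. With calls reaching 90% of women, the t-test and log-rank perform alike, and with all times observed the t-test is slightly stronger (87% v 85% power). It also keeps a difference in mean hours, which is how the outcome is worded. A reader might infer that a t-test is invalid for this outcome; the results do not support that. The gap is the unstated end of observation and handling rule. Log-rank is the safer choice because it needs no invented time and held 4-5% in every no-effect scenario with independent discharge.

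**The large figures rest on stacked assumptions.** This also stands. They need a 30 h median, early discharge, a 4 h gap in stay and observation that stops at discharge. None is in the documents. With shorter medians or longer stays the bias is smaller. A reader might infer that this trial has a 40-70% false-positive rate for stool; that is one assumed scenario, not a property of the plan.

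**The plan may already limit missing times.** The fluid rule mentions feces and the first day, and dropout is put at 10%. But the first governs intake and the second is a sample-size allowance, so neither says how many women will lack a stool time. The missing flow chart is a better objection: it could hold a follow-up time. The claim is therefore only that no readable text gives one.

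**It touches one secondary outcome.** Correct. A reader might extend the point to flatus, the primary outcome. The documents do not support that: "Patients will not be permitted to drink or eat, except for the drink offered by the researcher, till passing flatus" makes it likely that flatus occurs while the woman is still under observation. How the fluid rules relate to each other is a separate matter, not judged here.

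**Conclusion.** The point holds for time to first stool, as a change that should be made rather than one on which the trial depends. The readable plan has no end of observation and no rule for a woman with no recorded stool, and a comparison of means cannot be carried out for her without one.

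If observation ends at discharge and stays differ, either obvious rule can bias the result in either direction. If stays are equal, there is no false-positive problem, but a real difference is understated (4.5 h seen as 1.6 to 2.2 h at 36 h stays). The effect is large if about 20-45% of women lack a stool time and small once about 95% are observed. The documents do not say where this trial would fall. Confidence is medium, because the times are assumed and the flow chart cannot be read.

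**What to change.** Add to Data Analysis:

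> *Time to first stool (hours after surgery) will be analysed in all randomised women by allocated group, with Kaplan-Meier curves and a log-rank test. A woman with no recorded stool will be censored at the earlier of her last contact and [one fixed time after surgery, the same in both arms]. Medians with 95% confidence intervals and the number censored in each arm will be reported.*

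The sponsor should fill in the fixed time; the 96 h used above is only the value simulated.

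Where feasible, obtain stool times after discharge by telephone, using the contact list already provided for under Confidentiality. The calls do most of the repair. A woman who is not reached is still censored at discharge, which may depend on bowel recovery; hence the 7-9% false-positive rate without calls. If nearly all times are obtained, the planned t-test on means is also acceptable.

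**Cost.** One paragraph, one stated time, and the calls, which are new data collection and carry some recall error. Medians replace a mean difference for this outcome. If nearly all times are observed, log-rank costs about 2 points of power (87% − 85%). The primary test and the sample size are unchanged.

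### Age, parity, gestational age and cause of section are collected, but the only planned comparison is an unadjusted t-test, so any precision these variables offer goes unused

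*Combined protocol and SAP*

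**What the plan says.** The primary outcome is "A change in the number of hours for the patients to pass flatus for the first time after an elective caesarean". The Data Analysis section plans descriptive statistics and a single inferential method: "A t-test will be used to compare mean values of the two groups". No regression, analysis of covariance or stratified comparison is mentioned anywhere.

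Under History taking, the plan collects "Age, parity, gestational age at time of delivery" and "Cause of caesarean section", together with past medical history and drug intake. It does not say that any of these will be used in the comparison of groups.

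The Study design section describes allocation by numbered sealed envelopes and names no stratification factor. The Sample Size Justification states its basis as "considering the power of 90%, confidence 95% and significant level of 0.05", concludes that "the sample size needed is 544 cases", and reaches its total "with adding 10% for occasional cases' drop out so the total sample size would be 600 cases". It gives neither a target difference nor a standard deviation.

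**The concern.** Baseline information is collected on each woman and then used in neither the randomisation nor the analysis. If the recorded variables predict time to first flatus, the variation they explain stays in the error term of the t-test, and the confidence interval for the coffee effect is wider than it needs to be. A chance difference between the arms in one of these variables would also go uncorrected.

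A model named in advance uses whatever information the variables hold without affecting the type I error. An adjusted analysis first chosen after the data are seen would be open to the charge that the covariates were picked for their result.

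**Working it through.** **Inputs from the Sample Size Justification.** 544 women before dropout, so 272 per arm; power 90%; alpha 0.05; 1:1 allocation.

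**Inputs assumed.** Two-sided test (sidedness is not stated; 95% confidence suggests it), common SD, normal approximation, and R² from 0 to 20%. The documents give no R².

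**Step 1. The plan's own figure.** 544 cannot be reproduced, because the difference and the SD are missing. Solving backwards for the standardised difference:

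d = (1.960 + 1.282) × √(2/272) = 0.278.

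The dropout step is consistent with the stated 600: 544 × 1.10 gives 599 and 544/0.90 gives 605, both rounded up.

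**Step 2. Gain from adjustment.** Adjustment multiplies the residual SD by √(1 − R²). If 544 women give 90% power unadjusted, then

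power = Φ[(1.960 + 1.282)/√(1 − R²) − 1.960].

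The missing difference and SD drop out of this expression, so the result rests on R² and on the plan's 90% being right. The equivalent sample size is 544/(1 − R²), and the CI width factor is √(1 − R²).

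| Assumed R² | Power | Equivalent evaluable N | CI width factor |
|---|---|---|---|
| 0 | 90.0% | 544 | 1.000 |
| 2% | 90.6% | 555 | 0.990 |
| 5% | 91.4% | 573 | 0.975 |
| 10% | 92.7% | 604 | 0.949 |
| 20% | 95.2% | 680 | 0.894 |

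**Step 3. Cost of the added terms.** Age, parity and gestational age take three terms. Cause of section takes one fewer than its number of categories, so three categories make 5 terms in all and eight make 10. With k uninformative terms the variance rises by a factor of about 541/(541 − k):

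- k = 5: 541/536 = 1.009, so power is about 89.7%.
- k = 10: 541/531 = 1.019, so power is about 89.5%.

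The table is before this cost. Break-even R² is 1 − 536/541 = 0.9% for 5 terms and 1 − 531/541 = 1.8% for 10. At an R² of 2% with 10 terms the net variance factor is 0.98 × 1.019 = 0.998, so almost nothing is gained.

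**The case against.** The strongest case against acting is that no loss has been demonstrated. Nothing in the documents says that age, parity, gestational age or cause of section predicts time to flatus. The outcome has no pre-treatment value, which is often the most useful covariate. At an R² of 5% or less the gain is under 2 power points. The unadjusted comparison is unbiased under randomisation, and no stratification factor is being left out. All of this stands. It limits the point to a conditional gain in efficiency, but it does not remove the point, because the worst case is a loss of 0.3 to 0.5 power points.

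A reader might go further in four ways that the documents do not support.

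- **The sample is a known mix of emergency and planned sections.** The Patients section says "Patients will be recruited from emergency unit and inpatient wards", but that describes where women are recruited. The aim, research question, hypothesis and primary outcome all refer to elective section, while the inclusion criteria do not. That conflict is unresolved, and urgency is not a listed variable. If all sections are elective, an emergency/planned term would be constant.
- **Surgery duration is an available baseline covariate.** The inclusion criteria require only that it be under 90 minutes, and recording of the minutes is not listed. The plan does not say whether the envelope is opened before or after surgery. If before, duration is a post-randomisation variable, even though it precedes the first drink.
- **The narrower interval carries over to a time-to-event model.** The hazard ratio is non-collapsible. Adjustment changes what is estimated and generally does not narrow its interval, so the width factors apply to the linear model only.
- **Adjustment removes chance imbalance.** It corrects only for the covariates in the model, in the form in which they are modelled.

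**Conclusion.** The point holds as an efficiency and pre-specification improvement that should be made. Four variables are collected, none is used, and a better-specified primary analysis is available at little cost. The planned t-test remains valid, and a reader should not infer that it is biased or that its type I error is wrong.

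The benefit runs from a loss of 0.3 to 0.5 power points if the variables explain nothing to a gain of about 5 points at an R² of 20%. These figures assume 544 evaluable women, a two-sided 0.05 test, a linear model, and that the plan's 90% power at 544 is correct. Where the trial falls in that range cannot be determined from the documents.

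**What to change.** Replace the single t-test sentence in the Data Analysis section with the following elements.

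- **Primary analysis:** a linear regression of hours to first flatus on treatment group, with age, parity, gestational age and cause of section as covariates named in advance. Cause is grouped into a few categories defined before the data are seen.
- **Reporting:** the adjusted mean difference with its 95% CI.
- **Supporting analysis:** the unadjusted t-test.
- **Secondary outcomes:** the same model for hours to first bowel sound, hours to first stool and hours in hospital.

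Add surgery duration only if it is recorded and allocation follows surgery. Add an emergency/planned term only if the conflict over elective versus emergency sections is reconciled so that both are included.

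The cost is a few lines of text, a few degrees of freedom, and a decision on the coding of cause before analysis. The four core covariates are already listed for collection.
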